8.8.2.1 Serious Adverse Events Reporting

Study site personnel will report serious adverse events to the sponsor or designee using a serious adverse event report form in accordance with the information requested on the form. Serious adverse events reported to the investigator after the safety reporting period are to be reported to the sponsor if the investigator assesses the event as related to the study product.

If a subject dies, the serious adverse event report should include the cause of death as the event term (with fatal outcome), whether the event leading to death was related to study product, the autopsy findings if available, and any other supporting data (eg, death certificate, hospital/study site notes). The study site should also report the death to the sponsor by telephone.

Allergic reactions during food challenges that meet the criteria for serious will be reported as related to the procedure.

8.8.2.1.1 Expedited Reporting of Serious Adverse Events by the Sponsor and Periodic Reporting

The sponsor will determine whether a serious adverse event meets the criteria for expedited reporting to regulatory authorities, ECs, and investigators, as applicable in accordance with International Council for Harmonisation (ICH) E2A and ICH E6, and will ensure that reports are provided in compliance with the required timing.

Additionally, the sponsor will submit to regulatory authorities all safety updates and periodic reports as required by applicable national requirements including but not limited to ICH E6 and ICH E2F.

8.8.2.2 Adverse Events of Interest Reporting

Nonserious adverse events of interest will require rapid reporting (**within 24 hours**) regardless of severity, causality assessment, and where the event occurred (at the study site or elsewhere). Adverse events of interest include the following, and details for each are provided in the referenced sections:

- Systemic allergic reactions assessed as grade 2 or higher, including anaphylaxis ([Section 8.4](#) and [Section 8.4.1](#)).
- GI adverse events with prolonged dose interruption defined as withholding study product for > 7 consecutive days due to GI adverse events, or GI adverse events that result in early discontinuation ([Section 8.7.6.2.1](#)).
- Accidental/nonaccidental food allergen exposure ([Section 8.7.6.3](#)). Rapid reporting is required regardless of whether the exposure resulted in an adverse event.
- Severe adverse events ([Section 8.7.6.4](#)). Intended for adverse events that do not meet the criteria for other adverse events of interest.
- Use of epinephrine ([Section 8.7.6.5](#)). Use of epinephrine for a serious adverse event or other event requiring rapid reporting (eg, grade 2 or higher systemic allergic reaction, food allergen exposure) does not need to be reported separately.

Adverse events of interest meeting serious adverse event criteria are to be reported as serious adverse events.

8.8.2.3 Other Notable Events Reporting

Although pregnancy is not considered an adverse event, pregnancy must be reported on a pregnancy notification form. The pregnancy will be followed to delivery or termination, and reporting the outcome of the pregnancy and any postnatal sequelae in the infant will be required.

9 ASSESSMENT OF EFFICACY, SAFETY, AND HEALTH-RELATED QUALITY OF LIFE

9.1 Measures of Desensitization

9.1.1 Double-Blind Placebo-Controlled Food Challenge

The screening and exit DBPCFCs will each be conducted over 2 days and consistent with accepted food challenge procedures. Single doses of dried egg white protein and placebo will be conditionally tested at the screening DBPCFC (1, 3, 10, 30, 100, and 300 mg) and exit DBPCFC (3, 10, 30, 100, 300, 600, 1000, and 2000 mg) using a food challenge mixture administered sequentially at 20- to 30-minute intervals up to a single highest challenge dose of 300 mg at the screening DBPCFC (444 mg cumulative) and 2000 mg at the exit DBPCFC (4043 mg cumulative). The DBPCFC is described in [Appendix 1](#), including all requirements before, during, and after the DBPCFC. Full details are provided in the study manual.

9.1.2 Open Baked Whole Egg Food Challenge

The screening and exit open baked whole egg food challenges will be conducted within a single day and consistent with accepted food challenge procedures.

The open baked whole egg food challenge will conditionally test single doses of baked egg protein using a baked food product with egg (portions of 1 muffin equivalent to approximately 125, 250, 500, 500, and 625 mg baked egg protein), administered sequentially at 20- to 30-minute intervals up to a single highest dose of 625 mg of baked egg protein (cumulative 1 muffin that contains approximately one-third of one whole egg [equivalent to approximately 2000 mg baked egg protein]). The open baked whole egg food challenge is described in [Appendix 2](#), including all requirements before, during, and after the open baked whole egg food challenge. Full details are provided in the study manual.

9.2 Skin Prick Test

Egg white SPT mean wheal diameters will be measured to assess the immunomodulatory effects of study treatment. SPTs will include a positive control (histamine) and negative control (saline). SPT to aeroallergens (standard panel per local medical practice) will be performed at screening only. SPTs for egg white will be performed after antihistamines and other medications that could interfere with the assessment of an allergic reaction are discontinued for 5 half-lives of the medication, according to the schedules of activities. Details are provided in the study manual.

9.3 Safety and Other Assessments

9.3.1 Lung Function Tests and Assessments of Asthma Control

Lung function tests will be performed according to the schedules of activities ([Appendix 4](#), [Appendix 5](#)). Lung function tests include PEF for subjects aged ≥ 6 years and attempts of PEF for subjects aged 4 to 5 years. Spirometry will be performed if PEF shows a clinically

relevant reduction or for symptoms of clinical deterioration (eg, active wheeze on physical examination). Spirometry will be performed at screening for subjects aged ≥ 6 years with asthma.

For subjects with asthma, the evaluation of asthma severity will be assessed using the classification in [Table 17](#).

Asthma control in subjects with pre-existing asthma will be assessed using scores from the Asthma Control Test (ACT) ([Schatz, 2006](#)) and by the incidence of asthma rescue medication use. The ACT is a self-administered, 5-item questionnaire for subjects aged ≥ 12 years, used to evaluate the level of asthma control in the last 4 weeks. Each question is presented on a 5-point scale, with lower numbers indicating worse asthma control. A composite score of more than 19 indicates well-controlled asthma.

The Childhood Asthma Control Test (C-ACT) is a 7-item questionnaire used to evaluate the level of asthma control in subjects aged 4 to 11 years with pre-existing asthma ([Liu, 2007](#)). Subjects complete the first part of the questionnaire, which consists of 4 questions and a choice of 4 responses from 0 (worse asthma) to 3 (controlled asthma) for each question. The parent/caregiver may help the subject read or understand the question if needed, but only the subject should select the response. The parent/caregiver completes the second part of the questionnaire, which consists of 3 questions and a choice of 6 responses from 0 (worse asthma) to 5 (controlled asthma) for each question. Parents/caregivers are asked to recall asthma symptoms in the last 4 weeks and complete their portion of the questionnaire without influence from the subject's responses. A composite score of more than 19 indicates well-controlled asthma.

Table 17: Evaluation of Asthma Based on NHLBI Criteria

Classification	Intermittent (Step 1)	Persistent: Mild (Step 2)	Persistent: Moderate (Step 3 or 4)	Persistent: Severe (Step 5 or 6)
Symptoms	≤ 2 days/week	> 2 days/week but not daily	Daily	Throughout the day
Night-time awakenings				
Subject aged 0-4 years	0	1-2 times/month	3-4 times/month	> 1 time/week
Subject aged ≥ 5 years	≤ 2 times/month	3-4 times/month	> 1 time/week but not nightly	Often 7 times/week
Short-acting inhaled beta ₂ -agonist use	≤ 2 days/week	> 2 days/week, but not daily (and not more than once a day for subject ≥ 12 years)	Daily	Several times per day
Interference with normal activity	None	Minor limitation	Some limitation	Extremely limited
Lung function				
Subject aged 0-4 years	Not applicable	Not applicable	Not applicable	Not applicable
Subject aged 5-11 years	Normal FEV ₁ between exacerbations FEV ₁ $> 80\%$ predicted FEV ₁ /FVC $> 85\%$	FEV ₁ $\geq 80\%$ predicted FEV ₁ /FVC $> 80\%$ and $\leq 85\%$	FEV ₁ $\geq 60\%$ but $< 80\%$ predicted FEV ₁ /FVC $\geq 75\%$ and $\leq 80\%$	FEV ₁ $< 60\%$ predicted FEV ₁ /FVC $< 75\%$
Subject aged ≥ 12 years	Normal FEV ₁ between exacerbations FEV ₁ $> 80\%$ predicted FEV ₁ /FVC normal [1]	FEV ₁ $\geq 80\%$ predicted FEV ₁ /FVC normal [1]	FEV ₁ $\geq 60\%$ but $< 80\%$ predicted FEV ₁ /FVC reduced $\leq 5\%$ [1]	FEV ₁ $< 60\%$ predicted FEV ₁ /FVC reduced $> 5\%$ [1]

Adapted from [NHLBI, 2007](#).[1] Normal FEV₁/FVC by age: 8-19 years, 85%; 20-39 years, 80%; 40-59 years, 75%; 60-80 years, 70%.FEV₁, forced expiratory volume in the first second of expiration; FVC, forced vital capacity.

9.3.2 Eczema Area and Severity Index

The severity of clinical signs of eczema or atopic dermatitis in subjects with pre-existing eczema or atopic dermatitis will be assessed using the Eczema Area and Severity Index (EASI) scoring system. Higher scores indicate greater severity of eczema or atopic dermatitis.

9.3.3 TNSS Questionnaires

The Total Nasal Symptom Score (TNSS) is used to assess the severity of allergic rhinitis and will be administered only to subjects with pre-existing allergic rhinitis. The TNSS (short form) consists of 3 questions that address nasal obstruction, rhinorrhea, and nasal itch/sneezing ([Downie, 2004](#)). Each question has a choice of 4 responses that range from 0 (no symptoms) to 3 (severe symptoms). The subject is asked to recall symptoms over the last week to allow calculation of the symptom score.

9.3.4 PEESS v2.0 Questionnaire

The PEESS v2.0 ([Martin, 2015](#); [Franciosi, 2011](#)) is used to assess the frequency and severity of EoE symptoms in the last month and will be administered only for subjects with GI adverse events of interest ([Section 5.5.1](#), [Section 8.7.6.2.1](#)). The PEESS v2.0 consists of 4 domains (dysphagia, GERD, nausea/vomiting, and pain) and 20 items. Each item contains response options from 0 to 4. A higher total or domain score indicates more frequent and/or severe symptoms. The parent/caregiver of a subject aged 4 to 18 years completes the Parent Report for Children and Teens, and subjects aged ≥ 8 years complete the Children and Teens Report.

The PEESS v2.0 was not designed to establish a diagnosis of EoE; the use of this questionnaire to monitor the clinical course of GI symptoms must be considered exploratory. However, the PEESS v2.0 has shown content and construct validity ([Martin, 2015](#); [Franciosi, 2011](#)) and is a promising tool for following the clinical course of EoE or an EoE-like immune-mediated GI syndrome. The questionnaire has the potential to reveal trends toward symptomatic improvement or worsening that may otherwise go undetected.

9.3.5 Physical Examinations and Vital Signs

The investigator will perform physical examinations according to the schedule of activities.

Physical examinations will include an age-appropriate assessment of systems (eg, general appearance, head, eyes, ears, nose, mouth, skin, heart, lungs, lymph nodes, GI, genitourinary, neurologic, and skeletal) per standard of care at the study site or as clinically indicated by symptoms. Symptom-directed physical examinations will concentrate on target organ systems as clinically indicated by symptoms and may only focus on typical target organ areas for an allergic response, including the skin, oropharynx, and upper and lower respiratory, GI, and cardiovascular systems.

Vital sign measurements will include blood pressure, heart rate, and temperature.

Weight and height will be measured at specific visits according to the schedule of activities.

9.4 Health-Related Quality of Life Assessments

Health-related quality of life of subjects with hen egg allergy treated with AR201 or placebo will be assessed using scores from the Food Allergy Quality of Life Questionnaire (FAQQLQ) and Food Allergy Independent Measure (FAIM) questionnaires. FAQQLQ and FAIM questionnaires will be completed according to the schedules of activities ([Appendix 4](#), [Appendix 5](#)).

The FAQQLQ family of self- and proxy-report instruments is used to assess the effect of food allergy on the subject's quality of life. Evaluations by the subject and parent/caregiver (as applicable) use different forms by subject age group ([van der Velde, 2011](#); [Flokstra-de Blok, 2009a](#); [Flokstra-de Blok, 2009b](#); [DunnGalvin, 2008](#); [Flokstra-de Blok, 2008](#)). The number of items and domains vary by the instrument administered, and each item is scored on a 7-point scale from 1 (no impact) to 7 (extreme impact).

The FAIM self-report instruments are used to measure subject perception of food allergy severity and expectation of allergen exposure outcome, as evaluated by the subject using different forms by age group ([van der Velde, 2010](#)). The parent/caregiver versions include questions related to perception of disease severity and expectation of allergen exposure outcome for their child/teenager. The number of items and domains vary by the instrument administered, and each item is scored on a 7-point scale from 1 (limited severity perception) to 7 (greatest severity perception).

10 STATISTICAL METHODS

10.1 Statistical and Analytical Plans

The statistical methods and data presentations for reporting the study will be described in detail in the statistical analysis plan.

Randomization will be central and treatment allocation will be 2:1 (AR201 or placebo). Randomization will be stratified by baseline reactivity (tolerant or intolerant) to baked egg in an open baked whole egg food challenge at screening. Subjects who tolerate approximately 2000 mg cumulative baked egg protein without dose-limiting allergy symptoms will be considered baked egg tolerant. Subjects who do not complete the screening open baked whole egg food challenge for reasons other than dose-limiting symptoms and who have a clear clinical history of tolerance to baked egg may be considered baked egg tolerant after discussion with the medical monitor. All other subjects will be considered baked egg intolerant.

Data for demographic and baseline characteristics, efficacy, and safety will be summarized by treatment group (AR201 or placebo). Summary statistics will include the mean, number

of observations, standard deviation, median, minimum and maximum values for continuous variables, and frequencies and percentages for categorical variables.

Statistical significance is defined as $p < 0.05$ and tests will be 2-sided, unless otherwise specified. CIs will be calculated at the 95% level, reflecting a 2-sided type I error of 0.05.

The statistical methods and statistical analysis plan may be affected by a pandemic, epidemic, or other emergency not related to the study as described in [Appendix 3](#).

10.2 Analysis Populations

The intent-to-treat (ITT) population (ie, full analysis set) will be defined as all subjects who receive any part of one dose of study product. The ITT population will be used for all efficacy analyses unless otherwise specified, and analyzed according to randomized treatment. If no subjects receive the incorrect treatment, the ITT population will be the same as the safety population.

The completer population will be defined as all subjects in the ITT population who complete study treatment and have an evaluable exit DBPCFC (completion of at least the dried egg white food challenge day).

The per protocol population may be defined if it is sufficiently different from the completer population. The per protocol population will include all subjects in the completer population who have no major protocol deviations.

The safety population will be defined as all subjects who receive any randomized study treatment (ie, who receive any part of one dose of study product and complete one study visit). The safety population will be used for all safety analyses and analyzed according to treatment received.

10.3 Determination of Sample Size

A sample size of 84 subjects randomly assigned at a ratio of 2:1 to AR201 or placebo (56 AR201, 28 placebo) provides 89% power to demonstrate a significant treatment difference of at least 35% in desensitization response rate with AR201 compared with placebo for the primary efficacy endpoint of the proportion of subjects tolerating an at least 1000 mg single dose of dried egg white protein with no more than mild allergy symptoms during the exit DBPCFC. The sample size calculations are based on a 2-sided alpha of 0.05, and 2-sample comparison of binomial proportions with an assumed maximum desensitization rate of 60% in the AR201 group and 25% in the placebo group. Treated subjects who discontinue early from the study will be considered nonresponders.

10.4 Interim Analyses

No interim analyses are planned.

10.5 Analysis of Efficacy

10.5.1 Primary Efficacy Analyses

The primary objective assesses the efficacy of AR201 treatment in subjects aged 4 to 26 years, inclusive, with hen egg allergy.

The primary efficacy endpoint is the proportion of subjects treated with AR201 compared with placebo who tolerate a single highest dose of at least 1000 mg dried egg white protein with no more than mild allergy symptoms at the exit DBPCFC.

The ITT population and the Cochran-Mantel-Haenszel test will be used for these analyses. Subjects tolerating an at least 1000 mg single challenge dose of dried egg white protein will be considered responders; subjects who do not tolerate an at least 1000 mg single challenge dose of dried egg white protein will be considered nonresponders. Nonresponders will also include subjects who withdraw consent or discontinue early anytime before the exit DBPCFC.

Desensitization response rates and associated 95% CIs for each stratum will be presented for each treatment group using Wald CIs. The 95% CI for the treatment difference (desensitization rate for AR201 treatment minus desensitization rate for placebo) will be constructed by combining the stratum-specific differences using the Cochran-Mantel-Haenszel weights.

Full details will be provided in the statistical analysis plan.

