1 INTRODUCTION

1.1 Background

Hen egg allergy is a common and serious condition that disproportionately affects children and is associated with severe hypersensitivity reactions, including life-threatening anaphylaxis. The prevalence of egg allergy is estimated to be approximately 0.5% to 2.5% in Western countries (Loh, 2018). While egg allergy is typically outgrown, longitudinal studies have shown this may not occur until the second decade of life, with egg allergy persisting in approximately 20% of individuals aged 18 years (Clark, 2011; Savage, 2007). Higher peak egg-specific immunoglobulin E (IgE) levels, higher initial egg-specific IgE, and initial allergic reaction characteristics have been suggested to be predictive of persistence of egg allergy into adulthood (Sicherer, 2014; Lemon-Mule, 2008; Savage, 2007).

Two main egg allergy phenotypes are recognized in the clinic, allergy to both raw egg and baked egg, and allergy to raw egg only (Bartnikas, 2013; Tan, 2013; Turner, 2013; Lieberman, 2012; Osborne, 2011; Lemon-Mule, 2008). Approximately 20% to 30% of individuals with egg allergy are allergic to both raw egg and baked egg, and 70% to 80% of individuals with egg allergy are allergic to raw egg only (Tan, 2013; Turner, 2013; Lieberman, 2012; Osborne, 2011; Lemon-Mule, 2008). Allergy to well-cooked egg (baked egg) has been shown to resolve at a more rapid rate than allergy to uncooked egg (raw egg) (Clark, 2011).

The current standard of care for the management of egg allergy is dietary avoidance of egg and education of the patient/family on recognition and management of allergy symptoms and appropriate use of rescue medications (eg, epinephrine auto-injectors). Regular consumption of baked egg by patients with hen egg allergy who tolerate baked egg has been proposed to accelerate the development of tolerance to raw egg compared with avoidance (Leonard, 2012). However, it is not known whether the decreased time to resolution of hen egg allergy is due to regular consumption of baked egg by patients allergic to raw egg only or if these patients represent an egg allergy phenotype with a greater probability of outgrowing the egg allergy (Lambert, 2017; Dang, 2014).

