Concomitant medications review & instruction	Record all medications taken within 90 days before screening. Instruct subject to discontinue antihistamines and other medications that could interfere with the assessment of an allergic reaction 5 half-lives of the medication before the skin prick test and randomization. Review the prescribing information to determine the half-life of each medication for the subject's relevant age group.
Skin prick test	Measure mean wheal diameter for egg white, histamines, saline, and aeroallergens.

Activity	Comments
Laboratory Evaluations (Central)	Refer to the laboratory manual for sample collection and processing.
Hematology, immunology	Complete blood count with differential. Total IgE, egg white-specific and egg white component IgE; and egg white-specific IgG4.
Optional blood sample for potential future studies	At certain study sites only. Collect before the screening open baked whole egg food challenge.
Serum pregnancy test	For all females of childbearing potential.
Food Challenges and Eligibility Confirmation	
Open baked whole egg food challenge	Measure vital signs and assess signs/symptoms of allergic reaction just before each challenge dose, and at 15-20 minutes postdose if the dosing interval between challenge doses is prolonged.
DBPCFC	Perform within 14 days after the screening open baked whole egg food challenge. Consider waiting at least 2 days before conducting the first day of the screening DBPCFC if the open baked whole egg food challenge is positive, especially if rescue medications are given (eg, steroids). If circumstances create a safety risk (eg, an intercurrent illness), the first day of the DBPCFC may be delayed after discussion with the medical monitor. Conduct on 2 separate days within 7 days. Measure vital signs and assess signs/symptoms of allergic reaction just before each challenge dose, and at 15-20 minutes postdose if the dosing interval between challenge doses is prolonged.
Eligibility confirmation	Confirm eligibility after completion of all screening activities.

ACT, Asthma Control Test; C-ACT, Childhood Asthma Control Test; DBPCFC, double-blind, placebo-controlled food challenge; EASI, Eczema Area and Severity Index; FAIM, Food Allergy Independent Measure; FAQLQ, Food Allergy Quality of Life Questionnaire; ID, identification; Ig, immunoglobulin; NHLBI, National Heart, Lung, and Blood Institute; PEF, peak expiratory flow; TNSS, Total Nasal Symptom Score.

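### The primary CMH test is valid and its stated power reproduces, but it adjusts only for the baked-egg stratum; prespecifying the screening eliciting dose as a covariate could add about 1 to 4 points of power at little cost

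*Protocol*

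**What the plan says.** Protocol Section 10.5.1 fixes the primary test: "The ITT population and the Cochran-Mantel-Haenszel test will be used for these analyses". The confidence interval for the treatment difference is "constructed by combining the stratum-specific differences using the Cochran-Mantel-Haenszel weights". The test sentence does not name the stratum. Section 10.1 gives baked-egg reactivity (tolerant or intolerant) as the only randomisation stratum, and Section 10.5.2 names it for the severity endpoint, so no other reading is plausible. No other baseline value enters the primary analysis.

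Section 10.3 sizes the trial without stratum or covariate: "The sample size calculations are based on a 2-sided alpha of 0.05, and 2-sample comparison of binomial proportions". The response rates put in are 60% on active treatment, described as a ceiling, against 25% on control. It states that 84 subjects ("56 AR201, 28 placebo) provides 89% power to demonstrate a significant treatment difference of at least 35% in desensitization response rate"). Dropouts count against response: "Treated subjects who discontinue early from the study will be considered nonresponders".

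Two further baseline measures are taken in every subject:

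- **Screening DBPCFC.** Inclusion criterion 6 (Section 4.1) requires dose-limiting symptoms at 300 mg or less. Section 9.1.1 tests 1, 3, 10, 30, 100 and 300 mg.
- **Serum immunology.** Appendix 4 schedules "Total IgE, egg white-specific and egg white component IgE; and egg white-specific IgG4". Section 1.1 says that "higher initial egg-specific IgE, and initial allergic reaction characteristics have been suggested to be predictive of persistence of egg allergy into adulthood".

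**The concern.** Section 1.6 stratifies on baked-egg tolerance because it predicts spontaneous resolution. Section 1.1 makes a similar, more tentative statement about egg-specific IgE, and the screening DBPCFC is the baseline of the very measurement that defines the endpoint. Neither is used in the primary comparison.

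In a randomised trial, conditioning on a baseline value that predicts the outcome normally sharpens the comparison without more subjects or visits. With 56 and 28 subjects the trial has limited precision. Section 10.3 calls the 60% response rate a maximum, so there is not much slack if the true rate is lower. What is at stake is a modest amount of power and precision, not the validity of the result.

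**Working it through.** **Inputs from the protocol.** 56 AR201 and 28 placebo; 60% vs 25%; two-sided alpha 0.05 (Section 10.3).

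**Step 1: reproduce the stated power (pooled normal formula).**

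- Pooled rate = (56 × 0.60 + 28 × 0.25)/84 = 40.6/84 = 0.4833.
- SE under the null = √[0.4833 × 0.5167 × (1/56 + 1/28)] = 0.1157.
- SE under the alternative = √[0.60 × 0.40/56 + 0.25 × 0.75/28] = 0.1048.
- z = (0.35 − 1.96 × 0.1157)/0.1048 = 1.177, so power = 88.0%.

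Exact enumeration of the uncorrected chi-square gives 88.5%. The stated 89% stands.

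**Step 2: simulate the gain from one added covariate.** Marginal rates are held at 60% and 25%. The covariate is standard normal and independent of the stratum. All strengths are assumed, because the protocol gives none. Set A: 4,000 trials per case, 75% baked-egg tolerant, stratum log-odds 0.7. Set B: 8,000 trials per case, 70% tolerant, stratum log-odds 0.8. The tolerant shares and stratum effects are also assumptions.

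| Set | Odds ratio per SD | CMH on stratum | Score test, stratum + covariate | Gain (points) |
|---|---|---|---|---|
| A | 1.0 | 88.4% | 88.5% | 0.1 |
| A | 1.5 | 87.9% | 89.7% | 1.8 |
| A | 2.0 | 88.5% | 91.2% | 2.7 |
| A | 2.5 | 88.2% | 92.4% | 4.2 |
| B | 1.0 | 88.4% | 88.6% | 0.2 |
| B | exp(0.4) = 1.5 | 88.8% | 89.8% | 1.0 |
| B | exp(0.7) = 2.0 | 88.9% | 92.2% | 3.3 |
| B | exp(1.0) = 2.7 | 89.1% | 93.6% | 4.5 |

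The Monte Carlo SE of one power figure is about √(0.88 × 0.12/8,000) = 0.4 points in set B and 0.5 in set A.

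The screening dose has six levels and may correlate with the stratum. A further run with a six-level covariate, or with one correlated with the stratum, gave similar results: gains of about 1, 2 to 3 and 3 to 4 points at odds ratios of 1.5, 2.0 and 2.5. If the covariate differs by a full SD between strata (assumed), the gains are about 1.3, 1.9 to 2.6 and 2.7 to 4.0 points.

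**Step 3: cross-check by effective sample size.** Put N/(1 − R²) into the Step 1 formula, with R² assumed:

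- R² = 0.05: 84/0.95 = 88.4, power 89.7%.
- R² = 0.10: 84/0.90 = 93.3, power 91.3%.
- R² = 0.15: 84/0.85 = 98.8, power 92.8%.

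A companion simulation under the set B assumptions found the variance of the adjusted difference 3%, 7% and 15% below that of the unadjusted difference at odds ratios of 1.5, 2.0 and 2.7. That is consistent with gains of about 1 to 5 points.

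**Step 4: type I error at N = 84, two-sided, nominal 5%.** In set B (null rates 25% and 45%), across covariate strengths:

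- CMH: 4.4 to 5.6%.
- Adjusted score test, uncorrected: 5.0 to 6.0%.
- Standardised risk difference with a plain robust SE (companion simulation, null rate 25%): 5.2 to 6.8%.

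The score test runs slightly high, and the interval needs a correction more than the test does.

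**Step 5: which covariate is defined for everyone.** Eligibility requires a reaction at one of 1, 3, 10, 30, 100 or 300 mg. The eliciting dose therefore exists for every eligible subject, and its log is finite. The highest tolerated dose does not serve: a subject who reacts at 1 mg has tolerated no dose, and its log is undefined.

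**The case against.** The strongest case against raising this is that nothing is wrong. A CMH test stratified by the sole randomisation factor is standard, it pairs coherently with the CMH-weighted difference, and the power claim is sound. All of that stands.

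Several stronger readings are tempting, and the protocol does not support them:

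- **That the protocol shows these measures predict the endpoint.** Section 1.1 concerns natural persistence of egg allergy into adulthood, not passing a 1000 mg challenge after about nine months of treatment with dropouts counted as failures. No section links the screening DBPCFC threshold to exit response, and eligibility caps its range at 300 mg, which may weaken it. Its prognostic value is a reasonable expectation, not a documented fact.
- **That the power is free.** Step 4 shows slight inflation without a correction, and a model-based test is less transparent than CMH.
- **That chance imbalance biases the planned estimate.** Imbalance will occur: the SD of a standardised between-arm difference is √(1/56 + 1/28) = 0.23. Under randomisation this is variability, which the CMH test already allows for. Adjustment reduces that variability; it does not remove a bias.
- **That the plan lacks an adjusted analysis.** Section 10.5.1 leaves full details to the SAP, where a supportive adjusted analysis could sit. Only the choice of primary test is fixed in the protocol.

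What survives is narrow. The primary test as fixed uses one binary baseline factor, and a graded baseline of the same measurement is available for every subject.

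**Conclusion.** The point holds as an optional improvement. The planned CMH test is valid and the 89% power reproduces. Prespecifying the screening eliciting dose alongside the stratum would lift power from about 88% by about 1 to 4 points under an assumed odds ratio per SD of 1.5 to 2.5, with essentially no loss if the covariate predicts nothing. The size rests wholly on that assumed strength. The direction does not: two simulations under different assumptions and the effective-sample-size formula all point the same way. A reader should not infer that the trial is underpowered or that its primary result would be unreliable without the change.

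**What to change.** Amend Section 10.5.1 as follows:

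1. **Test.** Use the treatment score test from a logistic model with the baked-egg stratum and one covariate, the log of the screening DBPCFC eliciting dose (the dose that caused dose-limiting symptoms, 1 to 300 mg). Name this covariate alone; do not leave a choice between it and IgE.
2. **P-value.** Take it from re-randomisation within strata following the actual allocation scheme, or from another stated small-sample correction.
3. **Estimate.** Report the standardised risk difference with a small-sample-corrected 95% CI. State that the test governs the conclusion, since a model-based test and a marginal interval can disagree near the boundary.
4. **Sensitivity analysis.** Keep the planned CMH test and CMH-weighted difference unchanged.

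Section 3.3 unblinds each completing subject individually after exit. The covariate should therefore be fixed before the first such unblinding.

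The cost is a few lines of text and code, with no new subjects, visits or assays. The remaining downside is a model-based primary analysis in a small trial, which the correction and the retained CMH analysis are there to contain.
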